3. STUDY DESIGN

This is a single-center, randomized, open-label (unblinded), parallel-group controlled clinical trial evaluating the efficacy of a sequential multimodal intervention (structured physical exercise followed by SHP-based intergenerational activities) compared to nutritional education alone in community-dwelling elderly aged 60–75 years with physio-cognitive decline syndrome (PCDS).

The study duration per participant is 16 weeks, consisting of:

- Baseline assessment (week 0)
- Intervention period: 12 weeks of chair-exercise + 4 weeks of intergenerational activities (intervention arm) or continued education (control arm)
- Intermediate assessment (end of week 12)
- Final assessment (end of week 16)

Participants are randomized in a 1:1 ratio into two arms:

- Intervention arm (n=50): Nutritional education + 12 weeks structured chair-based exercise (PEROSI protocol, progressive frequency from 1 to 3 sessions/week, 60 minutes/session, supervised online) followed sequentially by 4 weeks SHP-based intergenerational activities (8 sessions, 2x/week, 45 minutes/session, paired 1:1 elderly-child using AMIR educational materials at selected orphanages).
- Control arm (n=50): Nutritional education only (2 personalized dietitian tele-conferences at weeks 1 and 11; 5 educational e-flyers at weeks 3, 5, 7, 13, and 15).

Randomization is computer-generated using permuted block randomization (block size 4), stratified if necessary, with allocation concealment managed by an independent third party. Blinding of participants and instructors is not feasible due to the nature of the behavioral interventions; however, outcome assessors for laboratory analyses (mBDNF) are blinded to group allocation where possible.

The trial follows intention-to-treat principles with per-protocol sensitivity analysis. Recruitment targets consecutive eligible elderly from community programs under the School of Medicine and Health Sciences at Atma Jaya Catholic University of Indonesia and the Archdiocese of Jakarta. Child participants (aged 5–8 years, n=50) are recruited from cooperating orphanages exclusively for the intervention arm.

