5.1 Investigational product/treatment

All participants (both arms) receive standardized nutritional education as a base intervention:

- Two personalized nutritional consultations via Zoom tele-conference with a certified dietitian (week 1 and week 11), focusing on balanced nutrition tailored to elderly needs.
- Five educational e-flyers on nutrition, physical activity recommendations for the elderly, and related topics (sent via mobile device at weeks 3, 5, 7, 13, and 15).

Intervention group (n=50 elderly + 50 children): In addition to nutritional education, participants receive a sequential multimodal intervention:

1. Structured physical exercise (weeks 1–12):

- Chair-exercise using the Indonesian Osteoporosis Association (PEROSI) protocol, adapted for tele-exercise.
- Sessions: 60 minutes duration, consisting of 10 min warm-up (light aerobic + flexibility), 30 min core (moderate aerobic, strength, balance), 5–10 min cool-down (light aerobic + stretching).
- Frequency progression: 1 session/week (weeks 1–2), 2 sessions/week (weeks 3–6), 3 sessions/week (weeks 7–12).
- Delivery: Online (tele-exercise) supervised by 1 certified PEROSI instructor and assisted by 1 research team member.
- Safety: Pre-session physical condition check; exercise termination based on Borg scale and American College of Sport Medicine (ACSM) guidelines for the elderly.

2. Social Heterochronic Parabiosis (SHP)-based intergenerational intervention (weeks 13–16):

- Group-based direct interaction: Each elderly participant paired 1:1 with one child participant (aged 5–8 years).

- Sessions: 8 total (2 sessions/week, 45 minutes each) conducted in-person at selected orphanages.
- Content: Educational and interactive activities using “Ayo Minum Air” (AMIR) materials from Indonesian Hydration Working Group (comic reading, simple gymnastics demonstration, educational games promoting hydration and healthy lifestyle).
- Organization: Elderly divided into 5 groups (10 elderly each); scheduled visits with research team accompaniment; facilities prepared for conducive interaction (seating, materials, spacing).
- Preparation: Training of Trainers (ToT) for elderly participants and research team during weeks 11–12 (3 sessions, 30 min each, outside exercise schedule).

Control Group

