7.2 Randomization, blinding, and treatment allocation

Randomization is performed after screening and baseline assessments using computer-generated permuted block randomization (block size 4). Allocation is managed by an independent third party (staff from the Department of Internal Medicine, School of Medicine and

Health Sciences at Atma Jaya Catholic University of Indonesia), not involved in the study. Sequence is concealed until assignment. Participants are allocated 1:1 to intervention or control arm.

Due to the behavioral nature of the intervention, blinding of participants, instructors, and research team is not possible (open-label design). However, laboratory analysts for mBDNF measurement are blinded to group allocation. Outcome assessors for physical measurements (grip strength, gait speed) are trained for consistency (inter-rater reliability tested with Kappa statistic).

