7.3 Study procedures

All procedures are performed by trained research personnel (principal investigator, assistants, certified instructors). Inter-rater reliability for grip strength and gait speed measurements is established prior to study start (Kappa evaluation on 50 elderly people between the principal investigator and assistants). Assessments are conducted at three time points: baseline (week 0), intermediate (end of week 12, post-exercise phase), and final (end of week 16, post-full intervention). Additional monitoring occurs as described.

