7.3.9 Questionnaires

All questionnaires are administered by trained research assistants through structured interviews to ensure consistency, especially for participants with limited literacy or visual impairment. Questionnaires are completed at baseline (week 0), intermediate (week 12), and final (week 16) assessments unless otherwise specified. Validated Indonesian versions are used where available.

- **Short Form-12 (SF-12):** Measures health-related quality of life with 12 items covering physical and mental component summaries (PCS and MCS). Scores are calculated using standard algorithms (range 0–100; higher scores indicate better quality of life). Primary focus on changes in physical and mental health domains.

- **EQ-5D-5L (EuroQol 5 Domains – 5 Levels):** Assesses five dimensions (mobility, self-care, usual activities, pain/discomfort, anxiety/depression) with 5 response levels each, plus a visual analog scale (EQ-VAS) for overall health state (0–100). Utility scores are derived using Indonesian value sets if available.
- **Geriatric Depression Scale-15 (GDS-15):** Screens for depressive symptoms with 15 yes/no items (score range 0–15; ≥5 suggests depression). Used for monitoring psychological well-being and exclusion criteria confirmation.
- **De Jong Gierveld Loneliness Scale (Indonesian version):** 11-item scale measuring emotional and social loneliness (range 0–11; higher scores indicate greater loneliness). Helps evaluate the impact of social isolation and potential benefits from intergenerational activities.
- **Physical Activity Scale for the Elderly (PASE):** Assesses leisure, household, and occupational physical activity over the past week. Scores are calculated based on frequency, duration, and intensity weights (higher scores indicate greater activity level). Administered to monitor baseline activity and changes.
- **Mini Nutritional Assessment (MNA) – Full version:** 18-item tool including anthropometric measures, global assessment, dietetic assessment, and subjective items (maximum 30 points: ≥24 normal, 17–23.5 at risk, <17 malnourished). Complements nutritional education intervention.
- **Charlson Comorbidity Index (CCI):** Calculated from medical history (19 conditions weighted 1–6 points) to quantify comorbidity burden and adjust for confounding in analyses.

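### Section 7.2 rules out blinding the research team for a reason that covers only participants and instructors, so nothing stops staff who know the allocation from measuring frailty, grip, gait and cognition at weeks 12 and 16

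*Combined protocol and SAP*

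**What the plan says.** On who can be blinded, the protocol gives three different accounts.

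- Section 7.2: "blinding of participants, instructors, and research team is not possible (open-label design", with the behavioural nature of the intervention as the reason.
- Section 3: the same reason, but applied only to participants and instructors.
- Section 5 (opening paragraph): investigators and participants will both be blinded.

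On who is masked, only the laboratory is named. Section 3 has "outcome assessors for laboratory analyses (mBDNF) are blinded to group allocation where possible"; Section 7.2 drops the qualifier and has "laboratory analysts for mBDNF measurement are blinded to group allocation".

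On who measures, Section 7.3 opens with "All procedures are performed by trained research personnel (principal investigator, assistants, certified instructors". Section 7.3.9 adds "All questionnaires are administered by trained research assistants through structured interviews". Section 7.3.5 gives MoCA-Ina to a trained assessor and does not mention masking. For grip and gait, Section 7.2 offers "Outcome assessors for physical measurements (grip strength, gait speed) are trained for consistency", and Section 7.3 describes a "Kappa evaluation on 50 elderly people between the principal investigator and assistants".

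On who delivers, Section 5.1 has exercise sessions "supervised by 1 certified PEROSI instructor and assisted by 1 research team member" and the research team accompanying the orphanage visits. Section 7.3.8 has a research assistant logging exercise attendance, and the research team supervising the intergenerational sessions and making the counselling calls.

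**The concern.** A behavioural intervention cannot be hidden from those who receive or teach it. It can be hidden, at least in part, from someone who meets the participant only to test them. Section 7.2 extends the infeasibility to the whole research team without a further reason, and so gives up a protection that the design does not rule out.

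The exposed outcomes leave room for influence. Grip is a maximal-effort test, gait depends on how the walk is cued, and MoCA-Ina and the questionnaires are given face to face. Grip and gait also decide two of the five CHS frailty items, and frailty is one of the two primary endpoints. If assessors know the allocation, a favourable result on any endpoint except mBDNF cannot be separated from a favourable shift in measurement, and no later analysis can recover the difference.

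**Working it through.** **1. Which endpoints have a masked assessor?** Sections 7.1.1 and 7.1.2 list six between-arm endpoints.

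| Endpoint | Measured by | Masking stated |
|---|---|---|
| Frailty, CHS (primary) | research personnel (7.3) | none |
| mBDNF (primary) | laboratory (7.2, 7.3.3) | yes |
| Grip strength | trained assessors (7.2) | none |
| Gait speed | trained assessors (7.2) | none |
| MoCA-Ina | trained assessor (7.3.5) | none |
| SF-12 | research assistants, interview (7.3.9) | none |

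One of six is protected.

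**2. Is delivery kept apart from measurement?** Sections 5.1 and 7.3.8 place the research team in exercise sessions, orphanage visits and calls. Sections 7.3 and 7.3.9 place the same categories of staff in outcome assessment. No section separates the two. Two details add to this:

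- Section 7.4 puts the adherence review and the intervention-arm preparation for the intergenerational phase in the same week 12 visit as grip, gait, frailty and MoCA-Ina. The visit itself can reveal the arm.
- The principal investigator takes part in the grip and gait reliability exercise (7.3). Under Section 11.2 the same role visits the orphanages and reviews attendance logs monthly.

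**3. Which time points are exposed?** Section 7.2 places randomization after baseline assessment, so baseline is unaffected. Weeks 12 and 16 are exposed.

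**4. The plan's sample size.** Section 4.5 gives a largest requirement of 42 per group at two-sided 5% and 80% power. Section 7.6 allows up to 15% drop-out. 42 / (1 − 0.15) = 49.4, rounded up to 50 per group, as stated. For a comparison of two means, 42 per group corresponds to a standardized difference of (1.960 + 0.842) × √(2/42) = 0.61 SD.

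**5. Illustration of bias.** The documents give no bias size, so the shift b is an assumption: the recorded change in one arm moves by b SD and there is no true effect. With n evaluable per arm, the noncentrality is δ = b / √(2/n), and the two-sided rejection probability is [1 − Φ(1.96 − δ)] + Φ(−1.96 − δ).

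Example, n = 42 and b = 0.2: δ = 0.2 / 0.218 = 0.917; 0.1484 + 0.0020 = 0.1504.

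| Assumed shift | 42 per arm | 50 per arm |
|---|---|---|
| 0 | 5.0% | 5.0% |
| 0.1 SD | 7.4% | 7.9% |
| 0.2 SD | 15.0% | 17.0% |
| 0.3 SD | 28.0% | 32.3% |

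A shift of 0.2 SD is about one third of the 0.61 SD difference (0.2 / 0.61 = 0.33) and triples the error rate. This is a normal approximation to the t-test that Section 9 plans for continuous changes. It does not carry over directly to the frailty category.

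**The case against.** The strongest reply is that the protocol never says the same people deliver and measure. The sentence opening Section 7.3 covers the whole of that section, including intervention procedures, so instructors would be listed there anyway. The measurement-specific text names the principal investigator, assistants and a trained assessor, not instructors. The trial also declares itself open-label, baseline precedes randomization, and one primary endpoint is laboratory-blinded. All of this is correct. It limits the point to what the plan permits; it does not supply masking or a separation rule.

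Several stronger readings are tempting, and the documents do not support them.

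- *Session staff do measure their own participants.* There is no roster. The overlap is left open, not shown.
- *Pre-study training is the only safeguard for grip and gait.* Section 11.2 adds periodic calibration and co-assessments, and Section 7.3.4 standardizes both tests. These protect consistency; they do not address knowledge of allocation.
- *The counselling calls coach one arm.* Section 5.2 gives them identically to both arms. They matter only because a caller may learn the allocation.
- *A small timing error would carry a participant over the 1.0 m/s line and change an outcome.* That value is an eligibility criterion. Gait is analysed as a continuous change, CHS slowness uses a quintile, and the documents do not say that the walk is timed by hand.
- *Assessors control all five frailty items.* Grip and gait supply two, exhaustion is self-reported, and MoCA-Ina supplies none.
- *Section 7.2 is the settled position.* Section 5 says the opposite, and the two must be reconciled.

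**Conclusion.** The point holds as a permitted exposure. The plan rules out research-team blinding on a ground that does not reach outcome assessors, masks one of six between-arm endpoints, and contains no rule keeping delivery staff or staff who know the allocation away from week 12 and 16 measurement. One of the two primary endpoints is affected. The three blinding statements cannot all be true.

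The size is unknown. The range of about 7% to 28% for the false-positive rate rests on assumed shifts of 0.1 to 0.3 SD, 42 evaluable per arm and no true effect. It shows sensitivity and does not estimate bias in this trial.

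A reader might infer that masked assessors would solve the problem. They would reduce it only: participants stay unblinded, exhaustion and SF-12 are self-reported, and grip and gait depend on effort. It is still a cheap improvement, and it has to be in place before the week 12 visits because the bias cannot be corrected afterwards.

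**What to change.** In Sections 7.2 and 7.3:

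1. Bar from week 12 and 16 outcome measurement the instructors and anyone who helps run exercise, training-of-trainers or intergenerational sessions, makes the calls, or reviews adherence.
2. Assign grip, gait, CHS items, MoCA-Ina and questionnaires at those visits to named, already trained assistants who are not told the allocation.
3. Ask participants not to disclose their group, and record at each visit whether the assessor learned it.
4. Hold the week 12 adherence review and training-of-trainers preparation (Section 7.4) apart from testing, with different staff.
5. Reconcile the blinding statements in Sections 3, 5 and 7.2, giving for each role whether it is masked and why.

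Sample size stays at 50 per group. The cost is a protocol paragraph and less flexible rostering. The documents refer to assistants in the plural but give no staff numbers, so it is an assumption that there are enough to split. If there are not, the minimum is to exclude session staff from measurement and state why full masking is not feasible. Some accidental unmasking will remain, and the record in item 3 lets it be reported.

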7.3 Study procedures

All procedures are performed by trained research personnel (principal investigator, assistants, certified instructors). Inter-rater reliability for grip strength and gait speed measurements is established prior to study start (Kappa evaluation on 50 elderly people between the principal investigator and assistants). Assessments are conducted at three time points: baseline (week 0), intermediate (end of week 12, post-exercise phase), and final (end of week 16, post-full intervention). Additional monitoring occurs as described.

7.3.1 Anthropometry and Vital Signs

- Height: Measured using a stadiometer (or knee-height estimation if standing is difficult).
- Body weight: Measured with calibrated digital scale (light clothing, no shoes).
- Body Mass Index (BMI): Calculated as weight (kg)/height² (m²).
- Vital signs: Blood pressure (seated, average of 2 measurements), heart rate, respiratory rate (to rule out acute instability).

7.3.2 Nutritional Status

Mini Nutritional Assessment (MNA): Full version administered via interview (screening + assessment sections; maximum 30 points).

Dietary habits: Brief anamnesis on usual intake; no formal 24-hour recall unless needed for dietitian consultation.

7.3.3 Blood sampling and Laboratory analysis

- Venous blood draw (5–10 mL) from the antecubital vein by a trained phlebotomist.
- Timing: Fasting preferred but not mandatory; performed at baseline, week 12, and week 16.
- Processing: Serum separated by centrifugation, aliquoted, and stored at -80°C until batch analysis.
- Primary biomarker: Mature brain-derived neurotrophic factor (mBDNF) quantified using a commercial ELISA kit specific for the mature form (to avoid pro-BDNF cross-reactivity). Analysis performed in an accredited laboratory with blinding to group allocation.

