Participants in the control group will receive usual care according to existing community health services. They will not participate in the structured exercise or SHP-based intergenerational activities during the study period. However, they will continue to receive standard health education and routine activities available within their respective community settings.

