7. METHODS

7.1 Study parameters/endpoints

7.1.1 Main study parameter/endpoint

- Change in frailty syndrome status (assessed using Cardiovascular Health Study criteria: score 0 robust, 1–2 pre-frail, ≥3 frail) from baseline to week 16.
- Change in serum mature brain-derived neurotrophic factor (mBDNF) levels (measured by ELISA) from baseline to week 16.

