7.3.7 Intervention-specific procedures

- Nutritional education (both groups):
 - Tele-conference consultations (Zoom): Personalized meal planning by dietitian.
 - E-fliers: Digital delivery with confirmation of receipt.
- Structured exercise (intervention group):
 - Pre-session screening: Symptom query, vital signs if needed.

- Session monitoring: Borg Rating of Perceived Exertion scale; termination if excessive dyspnea, pain, dizziness, or hemodynamic changes.
- Intergenerational activities (intervention group):
 - Pre-session preparation: Facility check (seating, materials, spacing).
 - Session structure: Introduction, AMIR-based activities (comic reading, joint gymnastics, games), reflection.
 - Post-session: Brief feedback from the elderly and children.

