7.4 Study visits

Study visits are scheduled to minimize burden while ensuring complete data collection. Visits occur at community centers, participant homes (if needed), or orphanages.

- Screening/Baseline visit (week 0, 1–2 days):
 - Explanation of study, informed consent (elderly and orphanage for children).
 - Medical history, comorbidity assessment (CCI), medication review.
 - Full physical examination, vital signs, anthropometry.
 - Cognitive (MoCA-Ina), physical (hand-grip strength, gait speed), functional (IADL), frailty (CHS), nutritional (MNA), and psychological assessments.
 - All questionnaires (SF-12, EQ-5D-5L, GDS-15, PASE, loneliness scale).
 - Blood sampling.
 - Randomization (post-eligibility confirmation).
 - Nutritional education initiation (first tele-conference scheduling).

- Intermediate visit (end of week 12, post-exercise phase):
 - Repeat anthropometry, vital signs.
 - Physical performance (hand-grip strength, gait speed), frailty status.
 - Cognitive (MoCA-Ina) and selected questionnaires (SF-12, EQ-5D-5L, GDS-15, loneliness).
 - Blood sampling.
 - Adherence review; ToT preparation for SHP (intervention arm).
- Final visit (end of week 16):
 - Comprehensive repeat of baseline assessments (all physical, cognitive, functional, nutritional, psychological, and questionnaires).
 - Blood sampling.
 - Adherence summary, adverse event review.
 - Compensation distribution (transport reimbursement, snacks provision during study).
- Ongoing visits/activities:
 - Exercise: Weekly tele-sessions (intervention group).
 - Intergenerational: 8 in-person sessions at orphanages (weeks 13–16).
 - Nutritional: 2 tele-conferences + 5 e-flyers (both groups).
 - Monitoring calls.

Home visits arranged if mobility limits attendance.

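### The mBDNF draws have no fixed fasting state and no set or recorded interval since the last session, which adds noise in both arms and leaves room for an arm-related sampling difference at week 16

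*Combined protocol and SAP*

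**What the plan says.** Section 7.1.1 lists as a main endpoint "Change in serum mature brain-derived neurotrophic factor (mBDNF) levels (measured by ELISA) from baseline to week 16". On the conditions of the draw, section 7.3.3 says "Fasting preferred but not mandatory; performed at baseline, week 12, and week 16". Serum is then stored and assayed in batch, with the laboratory blinded to arm.

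Section 7.4 places the follow-up draws at the end of week 12 and the end of week 16. Neither section gives a time of day, a rest period or a minimum gap after a session, and neither asks for the last meal or last session to be recorded. The same holds for sections 5.1, 7.3, 7.3.7 and 7.3.8.

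Under section 5.1 the intervention arm has three exercise sessions a week in weeks 7 to 12. SHP sessions follow in weeks 13 to 16: "Sessions: 8 total (2 sessions/week, 45 minutes each) conducted in-person at selected orphanages". Section 7.3.7 describes their content as "AMIR-based activities (comic reading, joint gymnastics, games), reflection", and section 10.4 provides snacks and drinks at each one. Of the controls, section 5.1 says "They will not participate in the structured exercise or SHP-based intergenerational activities during the study period".

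Section 7.2 puts randomization after the baseline assessments. Section 9 compares changes between arms with an unpaired t-test or Mann-Whitney test and has no term for fasting state or time since a session. On location, section 7.4 says "Visits occur at community centers, participant homes (if needed), or orphanages".

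**The concern.** Two separate weaknesses follow from the text.

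1. **Noise.** Fasting state is free to vary from draw to draw within a person. Any effect of food on serum mBDNF then enters the change score as extra variance. This applies to both arms.
2. **A possible difference between arms.** Baseline blood is drawn before allocation, so it cannot depend on arm. By week 16 only one arm is attending scheduled sessions with some physical activity and refreshments. If some intervention draws follow such a session closely and the session shifts mBDNF for a short time, the shift goes into that arm's change score and is read as an effect of the 16-week programme. It could act in either direction.

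The plan's safeguards do not reach this. Assay blinding and batching act after the tube is filled. The analysis in section 9 does not adjust for sampling conditions, and because these are not recorded, no later sensitivity analysis could do so.

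Grip and gait are measured at the same visits and feed the frailty score, the other main endpoint. Testing them soon after a session raises the same question, although no size can be put on it from the documents.

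**Working it through.** **Inputs from the documents**
- Two-sided 5% level, 80% power, requirements of 9 to 42 per group (section 4.5).
- Dropout up to 15% (section 7.6).
- Two SHP sessions a week in weeks 13 to 16, intervention arm only (section 5.1).
- Primary mBDNF contrast: baseline to week 16 (section 7.1.1).
- No SD or expected difference for mBDNF is given, and no acute effect of food or activity.

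**The plan's own figure.** 42 / (1 − 0.15) = 49.4, rounded up to 50 per group. This reproduces the stated 50. After 15% dropout, 50 × 0.85 = 42.5, so 42 completers per arm is used below.

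**Which sessions lie near which draw.** Exercise ends with week 12, about four weeks before the primary draw. Exercise sessions are therefore close in time only to the intermediate draw. Only SHP sessions can fall close to the week-16 draw.

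**Bias at week 16 (assumptions: the visit falls on a random day of the week; a session-day draw carries an acute shift of *a* SD of change).**
- Share of intervention draws on a session day: 2/7 = 0.286.
- Bias = 0.286 × *a*.
- Standard error of the arm difference, in SD units: √(2/42) = 0.218.
- With no true effect, the chance of p < 0.05 is 1 − Φ(1.96 − bias/0.218) + Φ(−1.96 − bias/0.218).

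| Assumed shift *a* (SD) | Bias (SD) | Bias / SE | False-positive rate |
|---|---|---|---|
| 0 | 0 | 0 | 5% |
| 0.5 | 0.14 | 0.65 | 10% |
| 1.0 | 0.29 | 1.31 | 26% |

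This holds the SD of change at 1. A mixture of shifted and unshifted draws adds variance 0.286 × 0.714 × *a*² in the intervention arm. At *a* = 1.0 that is 0.204, the standard error becomes √(2.204/42) = 0.229, and 26% becomes about 24%.

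**Noise from mixed fasting (assumption: variance of change rises by 10% to 50%, equally in both arms).** The standardized difference that 42 per group detects with 80% power is (1.960 + 0.842) × √(2/42) = 0.611. The documents do not say that 42 is the mBDNF requirement, so this is illustrative. With variance multiplied by *v*, power is Φ(0.611/√(2*v*/42) − 1.96). For *v* = 1.1 it is 76.2%, and for *v* = 1.5 it is 62.8%.

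**The case against.** The strongest reply is that nothing in the documents shows an acute effect of food, exercise or an SHP session on serum mBDNF, so no bias has been demonstrated. That stands, and it is why the range above starts at zero.

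Several stronger readings are tempting, and the documents do not support them:

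- **That three exercise sessions a week distort the primary endpoint.** The corresponding share, 3/7 = 43%, belongs to the week-12 draw, for which section 9 names no separate analysis.
- **That optional fasting biases the comparison.** The rule is the same in both arms. Alone it gives noise, and it becomes bias only if fed or fasted state differs by arm.
- **That intervention participants are bled at orphanages.** The location sentence in section 7.4 covers every kind of visit, and that section counts the SHP sessions among them. Orphanages may be named for that reason alone. No section says that blood, grip or gait is taken there.
- **That only the intervention arm can be sampled after food or activity.** Controls keep their routine community activities (section 5.1), and section 7.4 mentions snacks at the final visit without limiting them to one arm. What is specific to the intervention arm is the scheduled sessions and the refreshments tied to them.
- **That the trial claims a sustained rise.** The hypothesis in section 2 concerns higher levels after 16 weeks and does not use that idea.

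It is also fair that 2/7 counts draws taken before a session on the same day, and that SHP may be light activity: section 5.1 speaks of demonstrating simple gymnastics, where section 7.3.7 has it done jointly. Both points would lower the figures. Neither removes the gap, because the plan would be followed correctly whether the draw came before the session, just after it or days later.

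**Conclusion.** The point holds as a gap in the control of sampling conditions for a main endpoint, not as a demonstrated bias. The plan permits avoidable within-person noise in both arms. It also permits an arm-related difference in conditions at week 16 through proximity to SHP sessions.

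Under a random visit day and an acute shift of 0 to 1.0 SD, the bias is 0 to 0.29 SD, and the false-positive rate with 42 per arm is 5% to about 26%. The shift and the visit-day pattern are both assumptions, and the true effect may be nil. A reader might infer that a positive mBDNF result would be an artefact; the documents do not support that. What they do show is that such a result could not be checked afterwards, because neither the last meal nor the last session is recorded. The change is cheap now and cannot be made once blood is drawn, so it should be made before enrolment.

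**What to change.** - **Section 7.3.3:** require the same prandial state (overnight fast) and the same time-of-day window at all three draws in both arms. Take the draw on a day with no exercise or SHP session, after a minimum interval that the sponsor sets and justifies. The documents give no basis for a particular number of hours.
- **CRF:** record the time of the last meal and the date and time of the last session.
- **Section 9:** add a sensitivity analysis of mBDNF that excludes draws outside the rule.
- **Grip and gait:** hold these tests off session days too. They need not be done fasted.
- **Section 7.4:** state that outcome assessments take place at community centres or homes, with orphanages used for SHP sessions only.

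The cost is protocol and CRF wording, slightly tighter scheduling and three fasting visits per participant. Scheduling needs most care at the end of week 12, when exercise runs three times a week and SHP starts the following week; the sponsor should check that the chosen interval fits there.
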